To evaluate the safety and acceptability of the ShangRing for device-based circumcision in routine clinical settings, as a part of a comprehensive HIV prevention program for males aged 13 and older in Tanzania.

Evaluation Objectives

The specific objectives of the proposed implementation pilot is to:

- Describe/assess the safety of the ShangRing device by the occurrence of clinical adverse events (calculated as a rate), when circumcision is performed by trained mid-level providers;
- Ascertain capacity and required clinical capabilities of clinical staff of various cadres to carry out ShangRing procedures;
- Describe/assess male client and provider acceptability of the ShangRing device and process (e.g. need to return to the clinic for device removal, tolerance for leaving device in situ);
- Assess the percentage of clients clinically healed 6 weeks (42 days) following the removal of the device;
- Determine the time at which point all clients are physically healed following the removal of the device.

Primary Endpoint

The primary endpoint related to the goal and objectives of the evaluation is to:

- Measure the incidence of mild, moderate and severe AEs associated with ShangRing procedures including both procedure and post-procedure events, and all device-related malfunctions such as early spontaneous displacement. The primary endpoint will be assessed at device placement, at device removal, 3-days post removal, at the day 49 post-placement healing assessment, and at any unscheduled visit in that time frame. Adverse events will be measured and described in the following ways:
 - Total numbers and types of known AEs occurring among clients, including all severities of AEs (mild, moderate, severe) and serious AEs (see below), including detailed information about all instances of device displacement/detachment/self-removal/malfunction, need for medical attention or intervention, and final outcomes in those experiencing AEs.
 - Total number of clients with known AEs (may be different from above if clients experience multiple AEs), including all severities of AEs and serious AEs.

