 - Total number of clients who fail to return to the circumcision site (or site indicated by service providers) for recommended follow-up (whether removal visit or AE follow-up).
 - Proportion of all men receiving VMMC services at the evaluation sites who choose ShangRing method instead of surgical circumcision.
- Document provider acceptability of ShangRing, to be measured by the following:
 - Provider perceived ease of application, ease of removal, ease of clinical management of adverse events, and preferences in comparison to conventional circumcision methods.
- Document duration of procedures, and problems encountered during procedures and post-procedure care, to be measured by the following:
 - ShangRing application time will be measured, including the overall time the client is on the procedure table, and the time required for discreet application activities: client preparation time (including application of local anesthetic and sizing), marking and device application, and clean-up time.
 - ShangRing removal time will be measured, including the overall time the client is on the procedure table, the time required for discreet removal activities, and time for post removal instructions given to the client.
- The percentage of clients determined by a clinician to be clinically healed 49-52 days post-placement of the ShangRing device (42 days post-removal), and the time at which point all clients are clinically healed.
 - Healing will be documented by evaluation staff, who will take photographs of the client's genital area during the follow-up visits.
 - Healing will meet the definition of clinical healing after VMMC, defined as:
 - "Intact epithelium (unbroken skin) covering the wound as judged by the provider on visual inspection, meaning that none of the following are present: sutures, scabbing, drainage, moisture, gaps between epithelial edges or ulceration."²⁵

Evaluation Design

Overall Design

This implementation pilot is comprised of two phases: a training phase and the main implementation pilot. During the training phase clinicians at the participating sites will be trained in the use of the ShangRing device. Upon completion of the training phase, the main implementation pilot will begin. The implementation pilot is a single arm, open label, prospective cohort evaluation.

Description of Evaluation Populations and Catchment Areas

Shinyanga, Tanzania

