Sites should provide a brief orientation to other health centers in the catchment area. The purpose of this orientation is to provide these health centers with an overview of the pilot, to offer the health centers guidance on how to provide care for any pilot clients that may present to their clinic, and to request the health centers alert the pilot sites in the event that a client from the pilot seeks follow-up care from the center (i.e. in the case of the AE), and provide the health centers with contact information for implementation pilot staff in order to do so.

Sample Size, Data Collection and Analysis Timeline

The total sample size for this implementation pilot is 575 male clients at the selected sites in Shinyanga, Tanzania. Both HIV- and HIV+ men will be included in the sample. The sample size of 575 males is consistent with the framework for circumcision device introduction as proposed by the WHO (see appendix I below). Additionally, this sample size is powered to detect the occurrence of adverse events, which is estimated to be 2%. A minimum of 335 males are necessary for 95% confidence that the population proportion is within $\pm 1.5\%$ with an observed adverse event rate of 2%. An additional 240 males will be recruited for further confidence in the results, and to align with the WHO framework. The evaluation teams will enroll males until the 575 sample size figure is achieved. All 575 males to be considered for the data analysis will be enrolled upon completion of the training phase.

All data collection will begin as soon as the first circumcision of an enrolled client occurs. Data will continue to be collected until the country has performed 575 circumcisions with the ShangRing device, and all post-circumcision follow-up data collected from clients as detailed in this protocol is complete. After the 575 circumcisions and all follow-up information is collected, the analysis of data as described per the primary and secondary endpoints will begin. If after the country has finished 575 circumcisions, and wishes to conduct the analysis necessary to inform national policy for the purposes of implementing the ShangRing device on a wider scale, that country may continue to enroll clients, and the first 1000 circumcisions performed should be monitored through active surveillance, as detailed in the WHO framework, and the country should perform its own data analysis as needed.³¹

Supplies and Logistics

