The primary focus of the healing component is to determine the percentage of men that are clinically healed by day 49-52 following the placement of the ShangRing device (42-45 days post-removal), and to determine the time point post-placement at which all clients are clinically healed. All clients will be asked to return for a day-49 healing assessment, where a provider will review the clients wound to determine healing. As noted above, the wound will be considered healed if it meets the clinical definition of healing after VMMC, and will be indicated as such on the CRF. All clients will also have a photograph of their genital area taken at this visit to document healing. If the client is not clinically healed at the day-49 healing assessment, the client will be asked to return for another assessment in one week's time. Weekly healing assessments will continue until all clients are clinically healed.

Table 2: Implementation Pilot: Training and Implementation Phases

Evaluation Component	Sample Size	Endpoints	Methods and Data Collection
Phase 1: Training	Approximately 80-120, depending upon # of providers trained (at least 10 clients per provider)	
Primary endpoints:
 
 - Provider training needs - Provider acceptability 
Secondary endpoints:
 
 - Procedure and removal times 
Training Needs Component
 
Primary endpoints:
 
 - Provider proficiency with applying and removing the device 
Secondary endpoints:
 
 - Adverse events and device-related incidents - Procedure and removal times - Training satisfaction and needs of providers 	
Administered knowledge and theory based tests
 
Supervisor/doctor observation
 
Standardized forms to collect data on adverse events and device-related adverse events
 
Client records
 
Qualitative interview with providers
 
Photographs of the client's genital area, to be taken post-device removal (day 7), and at the day 49 healing assessment visit and at subsequent weekly healing visits

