All clients in the evaluation will be followed up at three points in time following ShangRing circumcision, on day 7 (device removal), on day 10 (three day post-removal AE assessment phone call), and day 49 (42 days/6 weeks following device removal). Ten percent of all clients will be brought in on day 28 (21 days/3 weeks following device removal) for in-depth qualitative interviews.

At the day 49 visit, a clinician will assess healing, an evaluation staff will photograph the client's genitals to document healing, and the client will receive counseling that will stress the following messages:

- If the wound is considered to be healed, the client will be informed that they may resume sexual activity and masturbation, but counseled on the need to continue safe sexual practices.
- If the wound is not considered healed, the clinician will offer ask the client to return in one weeks' time to assess healing and ensure the wound is fully healed. The client will also be advised to continue abstention from sexual activity and masturbation.
- If the client is not considered healed, and there is a clinically indicated reason to schedule further follow-up to take place before the next weekly visit, the evaluation staff will schedule such follow-up visits at a medically appropriate time.
- All sexually active clients will be offered a package of condoms to take home.

One week preceding the day 49 healing assessment visit (day 42) the client will receive a short reminder text asking that the client contact the site to confirm the appointment. The reminder text message will include client name and specify the name and phone number of the clinic reaching out to him. The text message will not include the purpose of appointment visit for which the reminder is sent. The client will be asked to confirm the appointment by either calling the clinic, or by replying with a text. If the client does not confirm the appointment within 3 days, (day 45), the client will be sent a second text. If the client still has not confirmed the appointment by day (47), the client will receive one phone call per day from day 47-49 until they have confirmed the appointment or indicated their intent not to come. If the client does not come in on day 49 for the healing assessment visit, and has not indicated his desire to withdraw from the evaluation, then the client will be established as lost to follow up.

Post Day 49 Healing Assessment Visits

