Baseline demographics and client characteristics will be presented in tabular format using descriptive statistics. Binary data such as adverse events will be presented as counts and percentages and the upper limit of the estimate of the AE rate (percent of clients with one or more AE) will be based on a two-sided 95% confidence interval. Adverse event rates will be compared descriptively with the reported rates of similar treatments reported in Tanzania and elsewhere, including: comparison against AE rates found in other studies of ShangRing, comparison against AE rates found in studies of other circumcision devices, and comparison against reported rates of AEs in studies of surgical circumcision. No formal hypothesis tests will be done comparing AE rates in this evaluation to other AE rates.

Adverse event rates will be presented by seriousness, severity, relation to device and outcome by site and by cadre. Continuous data will be represented by a mean, standard deviation, median, minimum and maximum together with 95% confidence intervals for the means. The number and percent of subjects who fail to complete the evaluation will be assessed. Time to withdrawal may also be assessed. The procedure time will be calculated. The first 15 procedures performed by each provider will be compared to the last 15 procedures by that provider with respect to procedure time, to evaluate whether procedure time is shortened with experience. All of the first and last 15 procedures evaluated will take place during the main implementation pilot phase. If a provider does not perform 30 total procedures following the training phase, then the first half of the total number of procedures performed will be compared against the last half. Adverse event rates from the training and post-training phases will also be reported, as well as an overall AE rate. Procedure times during the provider training phase will be tracked, but not used for comparisons. The differences in mean procedure times will be compared with a t-test or a non-parametric equivalent.

Standard statistical software packages R, Stata or SAS will be used for the analysis. No corrections for missing values will be imputed. The data will be analyzed and presented “as-is”.

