Client acceptability, time to return to normal activity, and clients' satisfaction with the post-circumcision cosmetic results will be summarized from data recorded on the evaluation surveys and during qualitative interviews conducted with 10% of randomly selected clients. Similarly, provider acceptability will be summarized from data recorded during qualitative interviews conducted with providers. Qualitative interviews will be digitally recorded and then transcribed by qualified staff. The recordings will be transcribed according to the local language used and then to English. The recordings will not be marked with any identifying information but with a unique identifier. Transcriptions will be reviewed electronically, using a qualitative interview analysis software such as Atlas.ti or NVivo, and analyzed for themes. The analysis of the qualitative data will be done through an inductive process where categories are identified as they emerge. Opinions generated by the 10% of clients included in the interviews will be used to tailor the messaging for future program implementation.

The percentage of men healed by day 49, and the time at which all clients are healed, will be reported from data recorded on the client CRFs. The proportion of men unsuitable for ShangRing MC will be extracted from an evaluation log maintained for the purpose of documenting the number of ineligibles and the reasons for their exclusion. Similarly, the number of men who decline ShangRing or who withdrawal will be reported as a proportion.

The photographs taken to document healing and adverse events will be used to supplement the analysis of both endpoints. Photographs will be reviewed only by evaluation project staff, and used to enhance the understanding of different adverse events and as evidence of the duration of the healing process. Photographs of all adverse events (if the client consents) will also accompany the AE reporting, to provide further clarity on these events. The photos will also be used by project staff to better educate ShangRing providers.

Long-Term Data Storage

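### The time at which all clients are healed is a sample maximum that any unfollowed client leaves unobserved; what can be reported is the latest healing day among men followed to healing, which equals or understates it.

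*Protocol*

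**What the plan says.** The endpoint appears in several places of the protocol.

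- Evaluation Objectives: "Determine the time at which point all clients are physically healed following the removal of the device".
- Secondary Endpoints: the percentage healed at day 49 to 52, "and the time at which point all clients are clinically healed". The Healing Component and Table 2 repeat it.
- Analysis Overview: "the time at which all clients are healed, will be reported from data recorded on the client CRFs".

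On follow-up, the Healing Component says "Weekly healing assessments will continue until all clients are clinically healed". It sets no end date and no rule for men who stop attending.

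Other sections provide for clients whose healing is not seen.

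- Client Withdrawal Criteria: a client who withdraws after placement is not replaced, his data stay in the analysis, and he is not asked back for the day 49 assessment.
- Follow-Up Visits: if a client does not attend on day 49 and has not withdrawn, "then the client will be established as lost to follow up".
- Appendix XII (Client Follow-Up Form): healing status is marked not applicable before day 42, so a client lost earlier has no healing record.
- Analysis Overview: "No corrections for missing values will be imputed", and the data are to be shown as they stand.

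The Photography section says that an analysis of healing times will inform pre-procedure counselling, including when sexual activity can resume.

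**The concern.** The day on which the last client heals is known only if every client is followed until he heals, and the protocol's own withdrawal and loss rules make that unlikely. Under a rule of no imputation, the figure that comes out of the CRFs is the latest healing day among those who kept attending. Printed under the endpoint's wording, it would read as a statement about all clients.

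The direction matters. Leaving men out of a maximum can lower it or leave it unchanged, never raise it. An early figure would feed into the healing times that the protocol wants for counselling messages and policy.

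**Working it through.** **The plan's own figure.** There is none for this endpoint. The only sample-size calculation concerns the adverse event rate.

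**Step 1: what is estimated.** Let T_i be the healing day of client i, with n = 575 ("The total sample size for this implementation pilot is 575 male clients at the selected sites in Shinyanga, Tanzania"). The endpoint is T_all = max(T_1, …, T_n). Let S be the clients followed to recorded healing. The CRFs give M = max of T_i over S. Since S is a subset of all clients, M ≤ T_all always, whatever the reason for loss.

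**Step 2: chance that S contains everyone.** The protocol gives no loss rate, so the rate d is an assumption, with independent losses. P(no client lost) = (1 − d)^575.

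| Assumed loss d | Expected clients lost | P(all 575 have a healing time) |
|---|---|---|
| 0.1% | 0.6 | 0.56 |
| 0.2% | 1.2 | 0.32 |
| 0.5% | 2.9 | 0.056 |
| 1% | 5.8 | 0.003 |
| 2% | 11.5 | 0.000009 |
| 5% | 28.8 | about 1.6 × 10⁻¹³ |

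Table 2 gives 455 to 495 for Phase 2. At 455 and 1% loss the chance is 0.99^455 = 0.010, so the choice of n does not change the picture.

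**Step 3: loss after day 49 only.** Assume 5% to 13% unhealed at day 49 (29 to 75 of 575), 40% to 60% of these healing per week (h), and 2% to 10% permanently lost at each weekly visit (d). Per unhealed client, P(lost before healed) = d / [1 − (1 − d)(1 − h)].

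- Most favourable corner: 0.02 / (1 − 0.98 × 0.4) = 0.033. P(at least one of 29) = 1 − (1 − 0.033)^29 = 62%.
- Least favourable corner: 0.10 / (1 − 0.90 × 0.6) = 0.217. P(at least one of 75) = 1 − (1 − 0.217)^75, nearly 100%.

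This leaves out men who withdraw or are lost before day 49.

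**Step 4: how often M falls short.** Assume 87.3% healed at day 49, 50% healing per week afterwards, and loss unrelated to healing speed among men unhealed at day 49. The 87.3% is borrowed from the field study in the protocol's HIV+ section, which reports it for HIV-negative men at 35 to 42 days, not day 49. In 20,000 simulated samples, M was below T_all in 1.6%, 3.7%, 7.7% and 15% of samples for losses of 2%, 5%, 10% and 20%. If loss is random, the printed day is therefore usually right, although nobody can verify it. If slow healers are lost more often, these figures are too low; the documents give nothing from which to quantify that.

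**Step 5: what loss does to a percentage.** With L men never observed healed, the percentage healed by the latest observed day lies between (575 − L)/575 and 100%. For L = 6 the lower bound is 569/575 = 99.0%; for L = 29 it is 546/575 = 95.0% (94.96%). These are statements the data can support.

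**The case against.** The case on the other side has weight. The evaluation is single-arm and descriptive. Clients agree at entry to return at day 49 and weekly until healed, and texts, calls and reimbursement support attendance. With complete follow-up the maximum is a correct description of the sample; by a distribution-free argument it would also support 95% confidence that at least 0.05^(1/575) = 99.5% of men heal by then. The percentage healed at day 49 to 52 is free of the sample-maximum problem, and nothing says that counselling will rest on the maximum alone. Estimators and censoring rules are ordinary SAP matter. What remains is that the protocol itself fixes the endpoint in a form its own follow-up rules are unlikely to deliver.

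Three stronger readings are not supported.

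- A reader might infer that the endpoint cannot be answered. A number can be reported, and with no loss it is the right one. The fault is that the wording claims more than that number shows.
- A reader might infer that losses are dropped without a trace. The Analysis Overview reports the number and percentage not completing and the proportion withdrawing, and the Client Withdrawal Criteria require reasons and timing. What is missing is a link from these counts to the healing result.
- A reader might object that a maximum grows with sample size. That is true in principle, but n is fixed at 575, and the 335 in the protocol is a precision minimum for adverse events, not a rival design. With 87.3% healed at day 49 and 50% healing per week, the expected maximum moves from day 96.2 at 335 to day 101.7 at 575, less than one weekly visit. At 30% per week it moves 10.6 days (137.5 to 148.1). All these rates are assumed.

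**Conclusion.** The point holds in a limited form. The endpoint is a sample maximum, and any client who withdraws, misses day 49 or stops weekly visits before healing leaves it unobserved. The reportable figure is the latest healing day among clients followed to healing, which equals or understates the value named. That M ≤ T_all needs no assumption.

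The size does rest on assumptions, since the protocol gives neither a loss rate nor a healing rate. Independent loss of 1% leaves a 0.3% chance that every client has a healing time; loss after day 49 alone leaves at least one man unobserved with probability 62% or more over the ranges tried. A shortfall is uncommon if loss is random (1.6% to 15% of samples in the scenario tried) and of unknown size if it is not. This concerns a secondary endpoint; the change should be made, but the primary safety endpoint is untouched.

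**What to change.** Restate the endpoint as the cumulative percentage healed at day 49 and at each weekly visit, among all clients with a device placed.

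- Estimate it with an interval-censored (Turnbull) or Kaplan-Meier method, with 95% confidence intervals. Add an upper percentile, such as the day by which 95% or 99% are healed, where estimable. If 95% are already healed at the first assessment, only an upper limit of day 49 can be given.
- State the number with a device placed who were never observed healed, next to the healing result.
- Censoring assumes that loss is unrelated to healing, and clients lost before any healing assessment add no information. So add a bound that counts all those never observed healed as not healed.
- Keep the latest observed healing day as a description, labelled as applying to clients followed to healing.
- Use one time origin. The objective counts from removal and the Healing Component from placement.

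The CRFs already collect what is needed. The cost is a change of wording, one extra standard analysis, and a headline less simple than a single day.
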